1.3 Exploratory Objectives

- 1.3.1 Compare RECIST v1.1 vs immune RECIST (iRECIST) in patients with CCS and CS on atezolizumab
- 1.3.2 Examine changes in PD-1/PD-L1 expression in the tumor microenvironment before and after atezolizumab treatment, and correlate treatment-induced changes with clinical response
- 1.3.3 Evaluate potential associations between atezolizumab activity and tumor genomic alterations

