11. MEASUREMENT OF EFFECT

11.1 Antitumor Effect – Solid Tumors

Patients should be re-evaluated for response at the end of Cycle 3 (before Cycle 4), and at the end of every two cycles thereafter (before every even-numbered cycle). Restaging scans may be performed less frequently for patients on study for more than 1 year (every three cycles for patients on study for more than 1 year; every four cycles for patients on study more than 2 years). Confirmatory scans should also be obtained ≥ 4 weeks following initial documentation of objective response.

Response and progression will be evaluated in this study using the international criteria proposed by the revised Response Evaluation Criteria in Solid Tumors (RECIST) guideline (version 1.1) [59]. Changes in the largest diameter (unidimensional measurement) of the tumor lesions and the shortest diameter in the case of malignant lymph nodes are used in the RECIST criteria.

Patients that are clinically well may continue on therapy following RECIST progression with new lesions or increase in target lesions, provided the criteria in Section [11.4](#) are met.

Response will also be explored using iRECIST (see Section [11.3](#)). Increasing clinical experience indicates that traditional response criteria such as RECIST may not be sufficient to fully characterize activity in the new era of target therapies and/or biologics. In studies with therapeutic antibodies, complete response, partial response, or stable disease has been shown to occur after an increase in tumor burden, characterized by progressive disease by traditional response criteria. Therefore, conventional response criteria may not adequately assess the activity of immunotherapeutic agents because progressive disease (by initial radiographic evaluation) does not necessarily reflect therapeutic failure. Long-term effect on the target disease must also be captured. The iRECIST criteria, by incorporating specific response patterns

that have been observed with immunotherapeutic agents, have been developed to address these issues and provide standardized response criteria for use with immunotherapy [60].

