11.2.4.3 Evaluation of Best Overall Response

The best overall response is the best response recorded from the start of the treatment until disease progression/recurrence (taking as reference for progressive disease the smallest measurements recorded since the treatment started). The patient's best response assignment will depend on the achievement of both measurement and confirmation criteria.

For Patients with Measurable Disease (*i.e.*, Target Disease)

Target Lesions	Non-Target Lesions	New Lesions	Overall Response	Best Overall Response when Confirmation is Required*
CR	CR	No	CR	≥ 4 wks. Confirmation**
CR	Non-CR/Non-PD	No	PR	≥ 4 wks. Confirmation**
CR	Not evaluated	No	PR	
PR	Non-CR/Non-PD/not evaluated	No	PR	
SD	Non-CR/Non-PD/not evaluated	No	SD	Documented at least once ≥ 4 wks. from baseline**
PD	Any	Yes or No	PD	no prior SD, PR or CR
Any	PD***	Yes or No	PD	
Any	Any	Yes	PD	

- * See RECIST 1.1 manuscript for further details on what is evidence of a new lesion.
- ** Only for non-randomized trials with response as primary endpoint.
- *** In exceptional circumstances, unequivocal progression in non-target lesions may be accepted as disease progression.

Note: Patients with a global deterioration of health status requiring discontinuation of treatment without objective evidence of disease progression at that time should be reported as “*symptomatic deterioration*.” Every effort should be made to document the objective progression even after discontinuation of treatment.

For Patients with Non-Measurable Disease (*i.e.*, Non-Target Disease)

Non-Target Lesions	New Lesions	Overall Response
CR	No	CR
Non-CR/non-PD	No	Non-CR/non-PD*
Not all evaluated	No	not evaluated
Unequivocal PD	Yes or No	PD
Any	Yes	PD
* ‘Non-CR/non-PD’ is preferred over ‘stable disease’ for non-target disease since SD is increasingly used as an endpoint for assessment of efficacy in some trials so to assign this category when no lesions can be measured is not advised		

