11.2.7 Response Review

For trials where the response rate is the primary endpoint, it is strongly recommended that all responses be reviewed by an expert(s) independent of the study at the study’s completion. Simultaneous review of the patients’ files and radiological images is the best approach.

11.3 iRECIST Response Assessment

Overall response will also be assessed using iRECIST as an exploratory endpoint, for comparison to RECIST v1.1.

Immunotherapeutics may result in infiltration of immune cells leading to transient increase in the size in malignant lesions, or undetectable lesions becoming detectable. Investigators should continue treatment, as appropriate, in the absence of unacceptable toxicity, until unequivocal disease progression. This is particularly important for patients in whom pseudoprogression may have occurred. Follow up response assessments must be continued until unequivocal disease progression has occurred.

The iRECIST criteria are identical to those of RECIST 1.1 in many respects but have been adapted to account for instances where an increase in tumor burden, or the appearance of new lesions, does not reflect true tumor progression.

Key differences are described below. All responses defined using iRECIST criteria are designated with a prefix. iRECIST time-point and best overall responses will be recorded separately. Unlike RECIST 1.1, iRECIST requires the confirmation of progression and uses the terms iUPD (unconfirmed progression) and iCPD (confirmed progression). Confirmatory scans should be performed at least 4 weeks, but no longer than 8 weeks after iUPD.

Confirming progression: Unlike RECIST 1.1, iRECIST requires the confirmation of progression and uses the terms iUPD (unconfirmed progression) and iCPD (confirmed progression). Confirmatory scans should be performed at least 4 weeks, but no longer than 8 weeks, after iUPD.

iCPD is confirmed if further increase in tumor burden, compared to the last assessment, is seen as evidenced by one or more of the following:

- Continued increase in tumor burden (from iUPD) where RECIST 1.1 definitions of progression had been met (from nadir) in target, non-target disease, or new lesions.
 - Progression in target disease worsens with an increase of at least 5 mm in the absolute value of the sum.
 - Continued unequivocal progression in non-target disease with an increase in tumor burden.

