Time-point (TP) iResponse

Target Lesions*	Non-Target Lesions*	New Lesions*	Time Point Response	
			No prior iUPD**	Prior iUPD**, ***
iSD	iUPD	No	iUPD	Remains iUPD unless iCPD confirmed based in further increase in size of NT disease (need not meet RECIST 1.1 criteria for unequivocal PD).
iUPD	Non-iCR/Non-iUPD	No	iUPD	Remains iUPD unless iCPD confirmed based on further increase in SOM of at least 5 mm, otherwise remains iUPD.
iUPD	iUPD	No	iUPD	Remains iUPD unless iCPD confirmed based on further increase in: 
 • previously identified T lesion iUPD SOM ≥ 5 mm and/or • NT lesion iUPD (prior assessment - need not be unequivocal PD)
iUPD	iUPD	Yes	iUPD	Remains iUPD unless iCPD confirmed based on further increase in: 
 • previously identified T lesion iUPD ≥ 5 mm and/or • previously identified NT lesion iUPD (need not be unequivocal) and/or • size or number of new lesions previously identified
Non-iUPD/PD	Non-iUPD/PD	Yes	iUPD	Remains iUPD unless iCPD confirmed based on increase in size or number of new lesions previously identified.

* Using RECIST 1.1 principles. If no PSPD occurs, RECIST 1.1 and iRECIST categories for CR, PR, and SD would be the same.
 
** in any lesion category.
 
*** previously identified in assessment immediately prior to this TP.
				

All patients will have their iBOR from the start of study treatment until the end of treatment

classified as outlined below.

iRECIST best overall response (iBOR)

TPR 1	TPR 2	TPR 3	TPR 4	TPR 5	iBOR
iCR	iCR, iPR, iUPD, NE	iCR, iPR, iUPD, NE	iUPD	iCPD	iCR
iUPD	iPR, iSD, NE	iCR	iCR, iPR, iSD, iUPD, NE	iCR, iPR, iSD, iUPD, iCPD, NE	iCR
iUPD	iPR	iPR, iSD, iUPD, NE	iPR, iSD, iUPD, NE, iCPD	iPR, iSD, iUPD, NE, iCPD	iPR
iUPD	iSD, NE	PR	iPR, iSD, iUPD, NE	iPR, iSD, iUPD, iCPD, NE	iPR
iUPD	iSD	iSD, iUPD, NE	iSD, iUPD, iCPD, NE	iSD, iUPD, iCPD, NE	iSD
iUPD	iCPD	Anything	Anything	Anything	iCPD
iUPD	iUPD	iCPD	Anything	Anything	iCPD
iUPD	NE	NE	NE	NE	iUPD

Table assumes a randomized study where confirmation of CR or PR is not required.
 
 • NE = not evaluable that cycle. • Designation "I" for BOR can be used to indicate prior iUPD to aid in data interpretation. • For patients with non-target disease only at baseline, only CR or non-CR/non-PD can be assigned at each TPR but is not shown in the table for ease of presentation. 					

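### The iRECIST best-response table in Section 11.3 waives confirmation of CR and PR, while RECIST 1.1 in this trial requires it, so exploratory objective 1.3.1 could partly measure the confirmation rule (minor)

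*Combined protocol and SAP*

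**What the plan says.** For RECIST 1.1, Section 11.2.4.3 states that the patient's "best response assignment will depend on the achievement of both measurement and confirmation criteria". Its table asks for confirmation of CR and PR at 4 weeks or later, with the footnote "Only for non-randomized trials with response as primary endpoint". This trial meets that condition. Cohorts are set by histology (Section 5), each follows a Simon two-stage design (Section 13.1), and the primary endpoint is ORR by RECIST 1.1 (Section 1.1). Section 11.1 adds: "Confirmatory scans should also be obtained ≥ 4 weeks following initial documentation of objective response".

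For iRECIST, Section 11.3 opens: "Overall response will also be assessed using iRECIST as an exploratory endpoint, for comparison to RECIST v1.1". This serves exploratory objective 1.3.1: "Compare RECIST v1.1 vs immune RECIST (iRECIST) in patients with CCS and CS on atezolizumab". The text of 11.3 requires confirmation of progression only. The sentence introducing the iBOR table begins "All patients will have their iBOR from the start of study treatment until the end of treatment" and says that this is classified by the table. The note under the table reads "Table assumes a randomized study where confirmation of CR or PR is not required". A further note says that the I designation "for BOR can be used to indicate prior iUPD to aid in data interpretation".

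**The concern.** The premise of the iBOR table does not hold for this trial. The two sets of criteria are meant to be compared, and the intended difference is how they treat apparent progression. If one requires a confirmed response and the other does not, a second difference enters. An excess of iRECIST responders could then be read as benefit after pseudoprogression when some of it comes only from counting responses that were never confirmed. Only the interpretation of objective 1.3.1 is at stake.

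**Working it through.** **Step 1: the two rules applied to the same patient.** iUPD is unconfirmed and iCPD confirmed progression.

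| Course | RECIST 1.1 (11.2.4.3) | iBOR (11.3) |
|---|---|---|
| CR at one scan, then progression that is later confirmed, with no earlier progression | CR not confirmed, so not a response | Row 1 permits iCR, iUPD, iUPD, iUPD, iCPD and gives iCR: a response |
| PR at one scan, then progression, with no earlier progression | PR not confirmed, so not a response | No row shows this; a response only through the table's general note |
| Progression first, then one PR, then progression again | Not a response | Rows 3 and 4 give iPR |

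The first two courses contain no pseudoprogression, so the disagreement comes from the confirmation rule alone. In the third, the handling of progression and the missing confirmation are mixed.

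**Step 2: the plan's own figures.** Section 13.1 has 9 adults in stage 1, a stop at no response, 17 in all, and success at 3 or more. Exact enumeration gives early stopping at a 5% rate of 0.95^9 = 0.630 (stated: at least .63), probability of a negative result at 5% of 0.953 (stated: at least .95), and power at 25% of 0.812 (stated: at least 81%). All three reproduce. They are context only, since the primary analysis uses RECIST 1.1.

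**Step 3: size per patient.** One such patient adds 1/17 = 5.9 points to the iRECIST rate in a full adult cohort and 1/9 = 11.1 points in one stopped at 9. Objective 1.3.1 does not restrict the comparison to adults or require it by cohort. With children included, the largest possible denominators under 13.1 are 9 + 2 = 11 for a stopped cohort (1/11 = 9.1 points) and 17 + 8 = 25 for a full one (1/25 = 4.0 points). Pooling three full adult cohorts gives 1/51 = 2.0 points.

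**Step 4: how often, as an illustration.** Inputs:
- r, the rate of first (not yet confirmed) responses: 5% and 25%, the rates used in 13.1.
- u, the share of first responses never confirmed: not in the documents; 10-30% is assumed.
- No pseudoprogression; adults only; the table's note applied to every first CR or PR.

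Let d = r × u be the chance that a patient is a discordant responder.

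P(no such patient in a cohort) = (1 − r)^9 + [(1 − d)^9 − (1 − r)^9] × (1 − d)^8

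This is the same whether the stage 1 stop uses first or confirmed responses. With the stop on confirmed responses:

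Expected number = 9d + 8d × {1 − [1 − r(1 − u)]^9}

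For r = 0.25 and u = 0.3, d = 0.075. P(none) = 0.075 + (0.496 − 0.075) × 0.536 = 0.301, so P(at least one) = 0.699. Expected number = 0.675 + 0.600 × (1 − 0.825^9) = 1.169.

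| r | u | P(at least one per cohort) | Expected per cohort |
|---|---|---|---|
| 5% | 10% | 5.7% | 0.059 |
| 5% | 20% | 10.8% | 0.115 |
| 5% | 30% | 15.5% | 0.168 |
| 25% | 10% | 33.6% | 0.405 |
| 25% | 20% | 55.7% | 0.796 |
| 25% | 30% | 69.9% | 1.169 |

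If only first responses that are iCR are affected (row 1), d becomes r × u × k, where k is the share of first responses that are CR. The documents give no k, and every figure in the table falls.

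**The case against.** The strongest reply is that the note is an unadapted caveat and was never meant as a rule for this trial. Section 11.3 calls the two sets of criteria alike in many respects, and its list of key differences does not include dropping confirmation of response. A footnote to the time-point table says the CR, PR and SD categories coincide when there is no pseudoprogression. On that view, a careful analyst would add confirmation unprompted. The intent may well have been equivalence. But the footnote governs time-point categories and not best overall response, the iBOR table is the only classification rule given, and row 1 behaves as the note says. The I designation marks earlier iUPD, does not show whether a response was confirmed, and changes no one's responder status.

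Three other objections stand and limit the point:
- No comparison statistic for 1.3.1 is specified. The problem arises if response rates or best-response categories are compared, which is plausible but not stated. Section 13.3 also promises caveats on exploratory results.
- No information is lost. Section 11.3 records iRECIST time-point responses, and 11.1 asks for confirmatory scans, so confirmed and unconfirmed iBOR can both be derived at analysis.
- The frequencies depend on an assumed unconfirmed share, adult-only denominators, and applying the note to every first response.

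**Conclusion.** The mismatch is real and minor. As written, 11.3 counts some unconfirmed responses that 11.2.4.3 does not, so a comparison of response under 1.3.1 would mix the confirmation rule with the handling of progression. Each affected patient moves a full adult cohort's iRECIST rate by 5.9 points. The number of such patients cannot be derived from the documents; under the stated assumptions the expected number per cohort runs from 0.06 to 1.17.

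A reader might infer more than this, and the documents do not support it:
- That the primary ORR or the Simon decisions are inflated. Both use RECIST 1.1, with its own confirmation rule.
- That PFS or DOR changes. Neither definition (11.2.5 and 11.2.6) uses iBOR.
- That treatment beyond progression is affected. Section 11.4 turns on confirmed progression and clinical criteria and does not use iBOR.
- That the table settles the case of a lone iPR. No row shows it; only the note covers it.
- That the frequencies are estimates for this trial. They are illustrations.

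**What to change.** In Section 11.3, replace the randomized-study note with: *iBOR of iCR or iPR requires confirmation at least 4 weeks after the criteria are first met, by the same rule used for RECIST 1.1 best overall response in Section 11.2.4.3.*

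Amend rows 1-4 of the iBOR table to match, and state that:
- any sequence without intervening iUPD, including iCR followed by iPR, takes the same category as the RECIST 1.1 best-response derivation;
- an unconfirmed iCR or iPR is classed as iSD if the SD minimum of 4 weeks from baseline is met. The first scheduled restaging, at the end of Cycle 3 (3 × 21 = 63 days, or 9 weeks), already meets it;
- unconfirmed iBOR is reported only as a labelled sensitivity result.

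The cost is protocol wording and a revised iBOR derivation. No scans are added, because 11.1 already asks for the confirmatory scan. Sample size, error rates and power do not change.

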11.4 Treatment Beyond RECIST Progression

During treatment, patients who show evidence of clinical benefit will be permitted to continue atezolizumab treatment following progression (as defined by RECIST v1.1), as long as the increase in disease burden does not meet the definition of confirmed PD by immune response criteria and if they meet all of the following additional criteria:

- Evidence of clinical benefit as assessed by the investigator and agreed upon by the Medical Monitor
- Absence of symptoms or signs (including worsening laboratory values) indicating unequivocal progression of disease
- No significant decline in performance status that can be attributed to disease progression
- Absence of tumor progression at critical anatomical sites (e.g., leptomeningeal disease) that cannot be managed by protocol-allowed medical interventions

The investigator must discuss with the patient the risks and benefits of treatment continuation after possible worsening disease and must document the patient's agreement to continue

receiving atezolizumab in the medical record.

If the investigator and patient decide to continue treatment, confirmatory scans should be performed at least 4 weeks, but no longer than 8 weeks after the assessment in which the RECIST 1.1 definition of PD was met. If this consecutive scan confirms PD, the patient should come off treatment.

12. STUDY OVERSIGHT AND DATA REPORTING / REGULATORY REQUIREMENTS

Adverse event lists, guidelines, and instructions for AE reporting can be found in Section [7](#).

12.1 Study Oversight

This protocol is monitored at several levels, as described in this section. The Protocol Principal Investigator is responsible for monitoring the conduct and progress of the clinical trial, including the ongoing review of accrual, patient-specific clinical and laboratory data, and routine and serious adverse events; reporting of expedited adverse events; and accumulation of reported adverse events from other trials testing the same drug(s). The Protocol Principal Investigator and statistician have access to the data at all times through the CTMS web-based reporting portal.

All Study Investigators at participating sites who register/enroll patients on a given protocol are responsible for timely submission of data via Medidata Rave and timely reporting of adverse events for that particular study. This includes timely review of data collected on the electronic CRFs submitted via Medidata Rave.

All studies are also reviewed in accordance with the enrolling institution's data safety monitoring plan.

12.2 Data Reporting

Medidata Rave is a clinical data management system being used for data collection for this trial/study. Access to the trial in Rave is controlled through the CTEP-IAM system and role assignments. To access Rave via iMedidata:

- Site staff will need to be registered with CTEP and have a valid and active CTEP-IAM account, and
- Assigned one of the following Rave roles on the relevant Lead Protocol Organization (LPO) or Participating Organization roster at the enrolling site: Rave CRA, Rave Read Only, Rave CRA (LabAdmin), Rave SLA, or Rave Investigator. Refer to <https://ctep.cancer.gov/investigatorResources/default.htm> for registration types and documentation required.
 - To hold Rave CRA or Rave CRA (Lab Admin) role, site staff must hold a minimum of an AP registration type,
 - To hold Rave Investigator role, the individual must be registered as an NPIVR or IVR, and

- To hold Rave Read Only role, site staff must hold an Associates (A) registration type.

If the study has a DTL, individuals requiring write access to Rave must also be assigned the appropriate Rave tasks on the DTL.

Upon initial site registration approval for the study in Regulatory Support System (RSS), all persons with Rave roles assigned on the appropriate roster will be sent a study invitation e-mail from iMedidata. To accept the invitation, site staff must log in to the Select Login (<https://login.imedidata.com/selectlogin>) using their CTEP-IAM username and password, and click on the *accept* link in the upper right-corner of the iMedidata page. Site staff will not be able to access the study in Rave until all required Medidata and study specific trainings are completed. Trainings will be in the form of electronic learnings (eLearnings), and can be accessed by clicking on the link in the upper right pane of the iMedidata screen. If an eLearning is required and has not yet been taken, the link to the eLearning will appear under the study name in iMedidata instead of the *Rave EDC* link; once the successful completion of the eLearning has been recorded, access to the study in Rave will be granted, and a *Rave EDC* link will display under the study name.

Site staff that have not previously activated their iMedidata/Rave account at the time of initial site registration approval for the study in RSS will also receive a separate invitation from iMedidata to activate their account. Account activation instructions are located on the CTSU website in the Rave section under the Rave resource materials (Medidata Account Activation and Study Invitation Acceptance). Additional information on iMedidata/Rave is available on the CTSU members' website in the Data Management > Rave section at www.ctsu.org/RAVE/ or by contacting the CTSU Help Desk at [name] or by e-mail at [contact].

12.2.1 Method

This study will be monitored by the Clinical Trials Monitoring Service (CTMS). Data will be submitted to CTMS at least once every two weeks via Medidata Rave (or other modality if approved by CTEP). Information on CTMS reporting is available at <http://www.theradex.com/clinicalTechnologies/?National-Cancer-Institute-NCI-11>. On-site audits will be conducted three times annually (one annual site visit and two data audits). For CTMS monitored studies, after users have activated their accounts, please contact the Theradex Help Desk at [contact] or by email at [contact] for additional support with Rave and completion of CRFs.

